9.2. Populations for Analysis

For the purposes of analysis, the following populations are defined:

- **Evaluable Population:** the Evaluable Population will include all subjects who receive at least 1 injection of study drug and have a histopathology and an immunohistochemistry report. The histopathology data of the 2 subjects whose abdominoplasty surgery was delayed due to COVID-19, will be analyzed separately.
- **Safety Population:** The Safety Population will include all subjects who receive at least 1 injection of study drug.

9.3. Statistical Hypotheses and Analyses

No statistical hypotheses and analyses are planned for the study. Subject narratives will be developed based on the histopathology and immunohistochemistry reports and safety data listings.

9.3.1. Histopathology and Immunohistochemistry

Histopathology and immunohistochemistry findings in the excised abdominal tissues injected with CCH will be compared to histopathology and immunohistochemistry findings in non-injected control tissue. Also, histopathology and immunohistochemistry findings in the excised abdominal tissues dosed twice with CCH will be compared to histopathology and immunohistochemistry findings in excised abdominal tissues dosed only once with CCH.

The pathologist, blind to the dosing schedule, will report any observed tissue differences from the control area (not injected).

9.3.2. Safety

All subjects who receive at least 1 dose of study drug will be included in the safety analyses. Subjects will be included in the safety analyses based on the actual treatment received.

9.3.2.1. Adverse Events

AEs will be coded using Medical Dictionary for Regulatory Activities (MedDRA) by preferred term within system organ class. The number of AEs and the number of subjects reporting AEs will be listed and summarized descriptively by body system, preferred term, severity, and causality. By-subject listings of AEs will be provided.

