
 ○ Multiple doses versus single dose with a [REDACTED] [REDACTED] ○ Multiple doses with a [REDACTED] versus multiple dose with a single injection technique. ○ Single dosing with a [REDACTED] versus single dosing with a [REDACTED] single injection technique. 	
 ● The change in histopathology and immunohistochemistry of tissue samples dosed with CCH multiple times relative to tissue dosed with CCH a single time with a [REDACTED] injection technique. 
 ○ Area 1 tissues relative to Area 2 for all groups. ● The change in histopathology and immunohistochemistry of tissue samples dosed with CCH multiple times with a [REDACTED] single injection technique relative to tissues dosed with CCH multiple times with a [REDACTED] technique. ● The change in histopathology and immunohistochemistry of tissue samples dosed with CCH a single time with a [REDACTED] single injection technique relative to tissues dosed with CCH a single time with a [REDACTED] technique.

 ● To assess the safety and immunogenicity of CCH injected in adult women undergoing an elective abdominoplasty surgery. 	
 ● Treatment-emergent adverse events (TEAEs). ● Adverse events of special interest (AESI). ● Anti-AUX-I antibodies, anti-AUX-II antibodies, and neutralizing antibodies analysis.

The primary objective will be met if histopathology and immunohistochemistry findings in the excised abdominal tissues dosed with CCH demonstrate change from histopathology and immunohistochemistry findings in non-dosed control tissue.

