8.2.1. Time Period and Frequency for Collecting AE and SAE Information

All SAEs and AEs will be collected by the investigator from the time of signing the informed consent through the Day 28/End of Study Visit or for 28 days after the last study treatment for those who early terminate. This will include any AEs that are ongoing at the time of completion/termination of the study. All ongoing AEs must be followed until resolution or for 28 days after the subject's last study treatment, whichever comes first. Injection site reactions will be considered resolved when the surgery is done due to surgical removal of the area.

All SAEs will be recorded and reported to the sponsor or designee within 24 hours, as indicated in Section 10.3. The investigator will submit any updated SAE data to the sponsor within 24 hours of it being available.

Investigators are not obligated to actively seek AEs and SAEs after conclusion of subject study participation. However, if the investigator learns of any SAE, including death, at any time after the subject has been discharged from the study, and the investigator considers the event to be at least possibly related to the study treatment or study participation, the investigator must promptly notify the sponsor.

The method of recording, evaluating, and assessing causality of AEs and SAEs and the procedures for completing and submitting SAE reports are provided in Section 10.3.

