10.3.1. Definitions

An AE is any unfavorable or unintended change in body structure (signs), body function (symptoms), laboratory result (eg, chemistry, ECG, X-ray, etc), or worsening of a pre-existing condition associated temporally with the use of the study medication whether or not considered related to the study medication. AEs will be captured once a subject has signed the informed consent. AEs include:

- Changes in the general condition of the subject.
- Subjective symptoms offered by or elicited from the subject.
- Objective signs observed by the investigator or other study personnel.
- All concurrent diseases that occur after the start of the study, including any change in severity or frequency of pre-existing disease.
- All clinically relevant laboratory abnormalities or physical findings that occur during the study.

A treatment-emergent AE (TEAE) is any condition that was not present prior to treatment with study medication but appeared following treatment, was present at treatment initiation but worsened during treatment, or was present at treatment initiation but resolved and then reappeared while the individual was on treatment (regardless of the intensity of the AE when the treatment was initiated).

A SAE is defined as an AE that:

- Results in death.
- Is immediately life-threatening (there is an immediate risk of death from the AE as it occurred; this does not include an AE that had it occurred in a more serious form may have caused death).
- Results in or prolongs an inpatient hospitalization (Note: a hospitalization for elective or preplanned surgery, procedure, or drug therapy does not constitute an SAE).
- Results in permanent or substantial disability (permanent or substantial disruption of one's ability to conduct normal life functions).
- Is a congenital anomaly/birth defect (in offspring of a subject using the study medication regardless of time to diagnosis).
- Is considered an important medical event.

Important medical events are defined as events that, based upon appropriate medical judgment, may jeopardize the subject and may require medical or surgical intervention to prevent one of the other serious outcomes. Examples of important medical events include allergic bronchospasm requiring intensive treatment in an emergency room or at home, blood dyscrasias or convulsions that do not result in inpatient hospitalization, or the development of drug dependency or drug abuse.

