4.4.1.1. Treatment-Emergent Adverse Events (TEAEs)

A TEAE is any condition that was not present prior to treatment with study medication but appeared following treatment, was present at treatment initiation but worsened during treatment, or was present at treatment initiation but resolved and then reappeared while the individual was on treatment (regardless of the intensity of the AE when the treatment was initiated).

The following rules will apply in cases where the start date of an AE is known:

- If the AE onset date is prior to first injection, then the AE will not be considered a TEAE.
- If the AE onset date is equal to or later than first injection, then the AE will be considered a TEAE.

Refer to Section 6.3.1.1 to identify TEAE status when start date of an AE is unknown.

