7.9.2. Adverse Events

Subject listings of all AEs, SAEs, AEs leading to study discontinuation, AEs resulting in drug interruption/withdrawn, AEs resulting in death, AESIs and AEs related to abdominoplasty will be provided.

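### Protocol Section 9.3.2.1 summarizes all AEs with no onset condition although the named safety endpoint is TEAEs, and the SAP names no TEAE table or listing

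*Protocol*

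**What the plan says.** Protocol Section 3 (and the Synopsis) gives three endpoints for the safety and immunogenicity objective: TEAEs, AEs of special interest (AESIs) and antibodies. Section 10.3.1 defines a TEAE, in its first limb, as "any condition that was not present prior to treatment with study medication but appeared following treatment".

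The planned AE summary is in Protocol 9.3.2.1: "The number of AEs and the number of subjects reporting AEs will be listed and summarized descriptively", broken down by body system, preferred term, severity and causality. It sets no treatment-emergent condition. Section 9.3.2 states who is included: "All subjects who receive at least 1 dose of study drug will be included in the safety analyses". Section 8.2.1 states when collection begins: "All SAEs and AEs will be collected by the investigator from the time of signing the informed consent". Section 5.4 allows up to 28 days between the start of screening and the first dosing visit.

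The SAP repeats the TEAE definition in 4.4.1.1 and makes it operational: "If the AE onset date is prior to first injection, then the AE will not be considered a TEAE". Section 6.3.1.1 adds rules for unknown dates. The AE outputs are then set out in 7.9.2, which begins "Subject listings of all AEs, SAEs, AEs leading to study discontinuation" and goes on to drug interruption or withdrawal, death, AESIs and abdominoplasty-related AEs. All of these are listings, and none is identified as treatment-emergent. SAP Section 8 says that no changes from the protocol are planned.

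**The concern.** The endpoint and the analysis are different quantities. The endpoint excludes anything that began before CCH was given and did not worsen or recur afterwards. The 9.3.2.1 summary includes such events for every subject who was later dosed. The SAP builds the classification that would separate the two, but names no output that counts or lists TEAEs.

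Under the protocol, then, a broader quantity than the endpoint is summarized. Under the SAP, no AE count is planned at all, and the departure from the protocol goes unrecorded. Either way, no named output reports the endpoint. In a study of about 10 subjects, a single misplaced subject is visible in any percentage.

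**Working it through.** **1. The plan's own figures.** Days from first dose to the Day 28 visit follow from the dosing days in Protocol 4.1:

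- Groups 1 and 4: 43 + 28 = 71
- Groups 2 and 5: 24 + 28 = 52
- Groups 3 and 6: 22 + 28 = 50

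This reproduces the stated 50 to 71 days per subject without screening. Enrollment also reproduces: 2 + 2 + 1 + 1 + 1 + 1 = 8, plus 2 replacements = 10.

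**2. Which events each rule admits.** Take a dosed subject with an AE that starts after consent and resolves before the first injection.

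| Rule | Is the event included? |
|---|---|
| Protocol 8.2.1, collection | Yes, collected from consent |
| Protocol 9.3.2, safety analyses | Yes, the subject was dosed |
| Protocol 9.3.2.1, summary | Yes, no onset condition |
| Protocol 3 and 10.3.1, endpoint | No |
| SAP 4.4.1.1, classification | No |
| SAP 7.9.2, all-AE listing | Yes |

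The summary and the endpoint therefore disagree on this event.

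**3. Length of the pre-dose window.** With s days of screening, the pre-dose share of AE collection time is s / (s + days from first dose to Day 28). The 14-day value is an assumption; 28 days is the protocol maximum.

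| Groups | s = 14 | s = 28 |
|---|---|---|
| 1 and 4 | 14/85 = 16.5% | 28/99 = 28.3% |
| 2 and 5 | 14/66 = 21.2% | 28/80 = 35.0% |
| 3 and 6 | 14/64 = 21.9% | 28/78 = 35.9% |

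These are shares of calendar time, not of events.

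**4. Effect on a subject count.** The Safety Population is every dosed subject, planned at about 10. One subject with only a pre-dose event moves a subject-level percentage by 1/10 = 10 points.

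The documents give no pre-dose AE rate. If p is the assumed chance that a subject has at least one pre-dose AE, the expected number affected is 10p, and the chance that at least one of 10 is affected is 1 − (1 − p)^10:

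| p (assumed) | Expected subjects | Chance of at least one |
|---|---|---|
| 5% | 0.5 | 40% |
| 10% | 1 | 65% |
| 20% | 2 | 89% |
| 30% | 3 | 97% |

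**5. Can a reader recover TEAE status from the planned variables?** SAP Table 5 has no TEAE variable. It defines AE Onset Day as start date minus surgery date plus 1, and Study Day as assessment date minus surgery date with no plus 1. Suppose a Group 1 subject is dosed exactly on Day −43 and has an event the day before. Its Study Day is −44, but its AE Onset Day is −44 + 1 = −43, which matches the nominal dosing day. The planned onset variable is not measured from first injection and can mislead at that boundary.

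**The case against.** The strongest reply is that SAP 6.1 promises listings of all CRF data and of any derived variables. TEAE status is derived under 4.4.1.1 and 6.3.1.1, so a flag may appear in the listings. The layouts that would settle this are in SAP Module 2, which is not available here. This stands in part. A reader might infer that the TEAE classification is used nowhere, and the documents do not support so absolute a claim. The generic sentence nevertheless names no TEAE flag, and it yields no count.

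Second, the SAP plans AE listings and subject narratives, not AE tables, so under the SAP there is no AE percentage for a pre-dose event to distort. That is correct, and it limits the 10-point figure to the protocol's summary. It also exposes the unrecorded difference between the two documents.

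Third, causality is part of the 9.3.2.1 breakdown, and a pre-dose event would ordinarily be judged not related. With about 10 subjects, dates can be compared by eye. Both points soften the consequence. But the overall counts would still include the event, and SAP 4.4.1.3 treats a missing relationship as related.

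Fourth, the AE definition in Protocol 10.3.1 refers to a temporal association with study medication, which might be read as excluding earlier events. The same section says that AEs are captured once consent is signed, so that reading does not hold.

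Three further inferences are tempting but unsupported:

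- **That 28% to 36% of reported AEs would be pre-dose.** Those are time shares at maximum screening. The protocol describes mainly injection-site reactions and surgical complications, which arise after dosing, so the share of events is probably smaller.
- **That one subject moves a percentage by 12.5 points (1/8).** Eight is the histopathology completion target. The two subjects with COVID-delayed surgery were dosed and remain in the safety analysis.
- **That a bruise from a screening blood draw would count as an AESI remote from the administration site.** No such site exists before the first injection, so the reading is strained.

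**Conclusion.** Wrong as written: the AE analysis in Protocol 9.3.2.1 does not match the endpoint in Section 3, and SAP 7.9.2 neither corrects it nor carries it over. Followed literally, the protocol's summary counts events in dosed subjects that began up to 28 days before any CCH, and no named output in either document reports TEAEs.

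The size is modest. No hypothesis is tested, safety is a secondary objective, and only descriptive reporting is affected. About 10 percentage points per affected subject is the right scale, assuming a Safety Population of about 10 and that the protocol's summary is produced. How many subjects would be affected cannot be stated from the documents.

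**What to change.** **Protocol 9.3.2.1.** Replace the AE summary with the number of TEAEs and the number of subjects with TEAEs, and likewise treatment-emergent AESIs, by body system, preferred term, severity and causality in the Safety Population. State that AEs starting before the first injection are listed only. Pre-existing conditions that worsen are not lost, because Protocol 8.2 already dates such an AE from the worsening.

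**SAP 7.9.2.** Add the same TEAE summary, or record in Section 8 that the protocol's AE summary has been removed and why. Show the TEAE flag and onset relative to first injection in every AE and AESI listing. Keep all events listed; a flag is enough, and the AESI listing need not be restricted.

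**Cost.** Wording in two documents, a flag from rules already in SAP 4.4.1.1 and 6.3.1.1, an onset day from dates already collected, and a short summary if it is restored. No new data, and no change to sample size or visits.

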9.3.2.2. Vital Signs

By-subject listings of vital signs will be provided.

9.3.2.3. Immunogenicity

Samples from Screening will be analyzed for anti-AUX-I and anti-AUX-II antibodies. Samples from Day 0 and Follow-up/End of Study visits will be analyzed for anti-AUX-I antibodies, anti-AUX-II antibodies, and neutralizing antibodies. Neutralizing antibodies will only be tested from anti-drug antibody (ADA) positive subjects. By-subject listings of anti-AUX-I and anti-AUX-II antibody levels, and neutralizing antibody results (positive/negative) will be provided.

9.4. Interim Analysis

No interim analysis is planned for this study.

10. SUPPORTING DOCUMENTATION AND OPERATIONAL CONSIDERATIONS

10.1. Appendix 1: Regulatory, Ethical and Study Oversight Considerations

10.1.1. Regulatory and Ethical Considerations

This clinical study is designed to comply with the ICH Guidance on General Considerations for Clinical Trials (62 FR 6611, December 17, 1997), Nonclinical Safety Studies for the Conduct of Human Clinical Trials for Pharmaceuticals (62 FR 62922, November 25, 1997), Good Clinical Practice: Consolidated Guidance (62 FR 25692, May 9, 1997) and 21 CFR parts 50, 54, 56 and 312.

The study will be conducted in full compliance with ICH E6, the FDA guidelines for Good Clinical Practice (GCP) and in accordance with the ethical principles that have their origins in the Declaration of Helsinki defined in 21 CFR, 312.120.

Approval by the IRB/IEC prior to the start of the study will be the responsibility of the investigator. A copy of approval documentation will be supplied to Endo along with a roster of IRB/IEC members that demonstrates appropriate composition or other documentation of assurance of appropriate composition per local and national regulations (eg, a Department of Health and Human Services [DHHS] Assurance Number will satisfy this requirement for IRBs in the US).

The study protocol, the ICF, advertisements, materials being provided to subjects, and amendments (if any) will be approved to IRB/IECs at each study center in conformance with ICH E6, CFR Title 21 Part 56, and any other applicable local laws. The investigator is responsible for supplying the IRB/IEC with a copy of the current Investigator's Brochure, Package Insert, or Summary of Product Characteristics, as well as any updates issued during the study. During the course of the study, the investigator will provide timely and accurate reports to the IRB/IEC on the progress of the study, at intervals not exceeding 1 year (or as appropriate), and will notify the IRB/IEC of SAEs or other significant safety findings, per the policy of the IRB/IEC. At the conclusion of the study, the investigator will submit a final report or close out report to the IRB/IEC and provide a copy to Endo.

Any amendment to this protocol will be provided to the investigator in writing by Endo. No protocol amendment may be implemented before it has been approved by the IRB/IEC and the signature page, signed by the investigator, has been received by Endo, except where the protocol is amended to eliminate or reduce the risk to the subject, the amendment may be implemented before IRB/IEC review and approval. However, the IRB/IEC must be informed in writing of such an amendment and approval obtained within reasonable time limits. Deviating from the protocol is permitted only if absolutely necessary for the safety or clinical management of the subject, and must be immediately reported to Endo.

The investigator will be responsible for supplying updated safety and/or study information to study subjects as it becomes available.

10.1.2. Financial Disclosure

Investigators and subinvestigators will provide the sponsor with sufficient, accurate financial information as requested to allow the sponsor to submit complete and accurate financial certification or disclosure statements to the appropriate regulatory authorities. Investigators are responsible for providing information on financial interests during the course of the study and for 1 year after the completion of the study.

10.1.3. Informed Consent Process

The ICF must be approved by the sponsor and the IRB/IEC before any subject provides consent. The investigator will provide the sponsor with a copy of the IRB/IEC-approved ICF and a copy of the IRB/IEC's written approval before the start of the study.

The ICF must contain all applicable elements of informed consent and the mandatory statements as defined by national and local regulations, including confidentiality.

At the Screening Visit (and at other times as may be required by the study or when changes are made to the consent form), subjects will read the consent form(s) and any privacy authorization as required by local and national regulations (such as the Health Insurance Portability and Accountability Act [HIPAA] authorization form), after being given an explanation of the study. Before signing the consent form(s) and the privacy authorization form (if applicable), subjects will have an opportunity to ask questions about the study and discuss the contents of these forms with study site personnel. The consent/assent process shall be recorded in source documents.

Subjects must assent understanding of and voluntarily sign these forms in compliance with ICH GCP and all applicable national and international regulations, before participating in any study-related procedures. Subjects will be made aware that they may withdraw from the study at any time for any reason.

All versions of each subject's signed ICF must be kept on file by the site for possible inspection by regulatory authorities and the sponsor. Signed copies of the consent form(s) and the privacy authorization form, if applicable, will be given to the subject.

The subjects will be made aware of their right to see and copy their records related to the study for as long as the investigator has possession of this information. If the subject withdraws consent and/or HIPAA authorization, the investigator can no longer disclose health information, unless it is needed to preserve the scientific integrity of the study.

10.1.4. Data Protection

Study subjects will be assigned a unique identifier by the sponsor or designee. Any subject records or datasets that are transferred to the sponsor will contain the identifier, subject initials, date of birth, and no other identifiable information.

The subject must be informed that her personal study-related data will be used by the sponsor in accordance with local data protection law. The level of disclosure (in accordance with local and/or national law) must also be explained to the subject.

The subject must be informed that her medical records may be examined by Clinical Quality Assurance auditors or other authorized personnel appointed by the sponsor, by appropriate IRB/IEC members, and by inspectors from regulatory authorities.

